Teclistamab, another BCMA BsAb, was approved in October 2022, based on results from the MajesTEC-1 trials; the ORR was 63.0%, and common adverse events included infections (76.4%), cytokine release syndrome (72.1%), anemia (52.1%), and neutropenia (70.9%). Elranatamab was approved in August of 2023, based on the results from the MagnetisMM-3 trial, a phase 2 trial aimed at assessing the efficacy of elranatamab monotherapy. The ORR was 61.0%, and common adverse events included infections (69.9%), cytokine release syndrome (57.7%), anemia (48.8%), and neutropenia (48.8%). While some published studies have assessed the real-world utilization of other BCMA BsABs such as teclistamab, the real-world usage of elranatamab has not been characterized. This study aims to describe the uptake and use of elranatamab subsequent to the August 2023 Food and Drug Administration (FDA) approval.

This noninterventional study is designated as a PASS and is conducted voluntarily by Pfizer.

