1	Antibiotics	Medical claim with an NDC, HCPCS, generic name or CPT code in the inpatient, non-IP, or pharmacy setting for antibiotic medications (dichotomous)	14 days prior to index date to 1 day prior to index date
1	Antifungal Medication	Medical claim with an NDC, HCPCS, generic name or CPT code in the inpatient, non-IP, or pharmacy setting for antifungal medications (dichotomous)	14 days prior to index date to 1 day prior to index date
1	Intravenous immunoglobulin	Medical claim with an NDC, HCPCS, generic name, CPT, or ICD-10 procedure code in the inpatient, non-IP, or pharmacy setting for intravenous immunoglobulin administration (dichotomous)	MM diagnosis to 1 day prior to index date

Objective	Variable	Definition	Assessment Period(s)
1	Other hematological malignancies	Medical claim with an ICD-10 code in the inpatient or non-IP setting for hematological malignancies other than MM (dichotomous)	MM diagnosis to 1 day prior to index date
1	Any non- hematological malignancy	Medical claim with an ICD-10 code in the inpatient or non-IP setting for non-hematological malignancies (dichotomous)	MM diagnosis to 1 day prior to index date
1	Plasma cell leukemia	Medical claim with an ICD-10 code in the inpatient or non-IP setting for plasma cell leukemia (dichotomous)	MM diagnosis to 1 day prior to index date
1	Bone lesions	Medical claim with an ICD-10 code in the inpatient or non-IP setting for bone lesions (dichotomous)	MM diagnosis to 1 day prior to index date
1	Peripheral neuropathy	Medical claim with an ICD-10 code in the inpatient or non-IP setting for peripheral neuropathy (dichotomous)	MM diagnosis to 1 day prior to index date
1	Any infection	Medical claim with an ICD-10 code in the inpatient or non-IP setting for any infection of the following types (dichotomous): COVID-19 Adenoviral pneumonia Cytomegaloviral pneumonitis COVID-19 pneumonia Other Pneumonia Upper respiratory tract infection Sepsis Cytomegaloviral infection Pneumocystis jiroveci pneumonia (PJP) Hepatitis C Hepatitis B Other infectious hepatitis Helicobacter pylori Candida esophagitis Urinary tract infection Sinusitis Bronchitis	MM diagnosis to 1 day prior to index date
1	Use of intravenous anti-infective	Medical claim with an NDC code generic name, CPT, or HCPCS code in the inpatient, non-IP, or pharmacy setting for anti-infective where the route	MM diagnosis to 1 day prior to index date

Objective	Variable	Definition	Assessment Period(s)

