Exploratory Obj 1	Other pneumonia ²	Medical claim with an ICD-10 code in the inpatient, non-IP, or pharmacy setting for pneumonia other than adenoviral or cytomegaloviral pneumonia (dichotomous)	Index date to end of follow-up, where follow-up will be based on last dose of elranatamab or teclistamab (e.g., 14 days after last recorded dose or 90 days after last recorded dose).
Exploratory Obj 1	Upper respiratory tract Infection ²	Medical claim with an ICD-10 code in the inpatient, non-IP, or pharmacy setting for upper respiratory tract infection (dichotomous)	Index date to end of follow-up, where follow-up will be based on last dose of elranatamab or teclistamab (e.g., 14 days after last recorded dose or 90 days after last recorded dose).
Exploratory Obj 1	Sepsis ²	Medical claim with an ICD-10 code in the inpatient, non-IP, or pharmacy setting for sepsis (dichotomous)	Index date to end of follow-up, where follow-up will be based on last dose of elranatamab or teclistamab (e.g., 14 days after last recorded dose or 90 days after last recorded dose).
Exploratory Obj 1	Cytomegaloviral infection ²	Medical claim with an ICD-10 code in the inpatient, non-IP, or pharmacy setting for cytomegaloviral infection (dichotomous)	Index date to end of follow-up, where follow- up will be based on last dose of elranatamab or teclistamab (e.g., 14 days after last recorded dose or

			90 days after last recorded dose).
Exploratory Obj 1	PJP ²	Medical claim with an ICD-10 code for PJP (dichotomous)	Index date to end of follow-up, where follow-up will be based on last dose of elranatamab or teclistamab (e.g., 14 days after last recorded dose or 90 days after last recorded dose).
Exploratory Obj 1	Hepatitis C ²	Medical claim with an ICD-10 code in the inpatient, non-IP or pharmacy setting for hepatitis C (dichotomous)	Index date to end of follow-up, where follow-up will be based on last dose of elranatamab or teclistamab (e.g., 14 days after last recorded dose or 90 days after last recorded dose).
Exploratory Obj 1	Hepatitis B ²	Medical claim with an ICD-10 code in the inpatient, non-IP or pharmacy setting for hepatitis B (dichotomous)	Index date to end of follow-up, where follow-up will be based on last dose of elranatamab or teclistamab (e.g., 14 days after last recorded dose or 90 days after last recorded dose).

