9.8. Quality Control

Clarify Health will code measures for cohort identification, outcomes, and other variables of interest based on codes and algorithms described in this protocol. This protocol will be strictly followed when conducting the analysis of this study. All cohorts developed, statistical analyses implemented, and tables completed will undergo quality control review by at least one additional analyst or scientist under the supervision of the Study Lead. The Study Lead will review all results tables and other final deliverables to confirm accuracy, logical flow, and appropriate format.

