	Clinical, Adverse event		E13.41, G57.70, G57.71, G57.72, G57.73, G59, G57.80, G57.81, G57.82, G57.83, G58.8, G58.9, G64., G61.0, M05.50, M05.511, M05.512, M05.519, M05.521, M05.522, M05.529, M05.531, M05.532, M05.539, M05.541, M05.542, M05.549, M05.551, M05.552, M05.559, M05.551, M05.552, M05.559, M05.571, M05.572, M05.579, M05.59, E08.40, E08.42, E09.40, E09.42, E10.40, E10.42, E11.40, E11.42, E13.40, E13.42, G13.0, G13.1, A36.83, A52.15, G63, M34.83, G62.1, G61.1, G62.0, G62.2, G62.82, G61.81, G62.81, G61.89, G62.89, G61.9, G62.9, H46.3, M54.10, M54.18, M79.2, R20.0, R20.1, R20.2, R20.3, R20.8, R20.9
Any infection	Baseline characteristic - Clinical	Claims data	An ICD-10 Diagnosis Code for any of the following types of infections. See the rows below for codes for each infection type. COVID-19, Adenoviral pneumonia, Cytomegaloviral pneumonitis, Other Pneumonia, Upper respiratory tract infection, Sepsis, Cytomegaloviral infection, Pneumocystis jiroveci pneumonia (PJP), Hepatitis C, Hepatitis B, Other infectious hepatitis, Helicobacter pylori, Candida esophagitis, Urinary tract infection
Use of intravenous anti- infective	Baseline characteristic - Clinical	Claims data	See "Antivirals" and "Antibiotics" above
Neutropenia	Baseline characteristic - Clinical, Adverse event	Claims data	ICD-10 Diagnosis: D70x
Hypercalcemia	Baseline characteristic - Clinical	Claims data	ICD-10 Diagnosis: E83.52
Hypoxia	Baseline characteristic - Clinical, Adverse event	Claims data	ICD-10 Diagnosis: J96.20, J96.11, J96.90, J96.01, J96.00, J96.10, J96.21, J96.91, I27.23, R09.02
Hepatotoxicity	Baseline characteristic - Clinical, Adverse event	Claims data	ICD-10 Diagnosis: K71.x
Renal failure	Baseline characteristic -	Claims data	ICD-10 Diagnosis: N17x, N18x, N19x, R34x, T82.4, Z49.02, Z99.2

	Clinical, Adverse event		
Amyloidosis	Baseline characteristic - Clinical	Claims data	ICD-10 Diagnosis: E85.4x, E85.8x, E85.9x
Hypertension	Baseline characteristic - Clinical	Claims data	ICD-10 Diagnosis: I10x-I15x, I16x
Extramedullary disease	Baseline characteristic - Clinical	Claims data	ICD-10 Diagnosis: C90.2x
CCI score	Baseline characteristic - Clinical	Claims data	See components below
Myocardial infarction	Baseline characteristic - Clinical	Claims data	ICD-10 Diagnosis: I21.x, I22.x, I25.2
Congestive heart failure	Baseline characteristic - Clinical	Claims data	ICD-10 Diagnosis: I11.0, I13.0, I13.2, I25.5, I42.0, I42.5, I42.6, I42.7, I42.8, I42.9, I43.x, I50.x, P29.0

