Rash	Adverse events	Claims data	ICD-10 Diagnosis: R21, D72.12
Angioedema	Adverse events	Claims data	ICD-10 Diagnosis: T78.3X, D72.118
Erythema	Adverse events	Claims data	ICD-10 Diagnosis: L53.0, L53.1, L53.2, L51, L52, L71.0, L71.1, L71.8, L93.0, L93.2, L49.0, L49.1, L49.2, L49.3, L49.4, L49.5, L49.6, L49.7, L49.8, L49.9, L00, L26, L30.4, L53.8, L92.0, L95.1, L98.2, L53.9
Muscle spasms	Adverse events	Claims data	ICD-10 Diagnosis: M62.83X
Musculoskeletal pain	Adverse events	Claims data	ICD-10 Diagnosis: M25.50, M25.522, M25.551, M25.552, M25.561, M25.562, M25.572, M25.579, M25.59, M25.612, M25.621, M25.629, M25.631, M25.641, M25.642, M25.662, M25.669, M25.671, M25.673, M25.674, M25.675, M25.676, M54.6, M54.81, M79.1, M79.12, M79.18, M79.621, M79.622, M79.631, M79.639, M79.641, M79.644, M79.646, M79.669, M79.671, M79.673, M79.675, M25.511, M25.512, M25.519, M25.521, M25.529, M25.531, M25.532, M25.539, M25.541, M25.542, M25.549, M25.611, M25.619, M25.622, M25.632, M25.639, M25.649, M25.651, M25.659, M25.672, M25.69, M25.671, M25.69, M25.672, M25.69, M25.672, M25.69, M25.672, M27.69, M27.603, M79.604, M79.605, M79.606, M79.609, M79.629, M79.632, M79.672, M79.674, M79.676
COVID-19	Adverse event - infection	Claims data	ICD-10 Diagnosis: U07. 1

COVID-19 pneumonia	Adverse event -	Claims	ICD-10: J12.82
Adenoviral pneumonia	infection Adverse event - infection	data Claims data	ICD-10 Diagnosis: J12.0
Cytomegaloviral pneumonitis	Adverse event - infection	Claims data	ICD-10 Diagnosis: B25.0
Other pneumonia	Adverse event - infection	Claims data	ICD-10 Diagnosis: A01.03, A02.22, A20.2, A21.2, A31.0, A37.01, A37.11, A37.81, A37.91, A43.0, A48.1, B01.2, B05.2, B06.81, B37.1, B38.0, B38.2, B39.0, B39.2, B58.3, B59, B77.81, J10.00, J10.08, J11.00, J11.08, J12.1, J12.2, J12.3, J12.81, J12.89, J12.9, J13, J14, J15.0, J15.1, J15.20, J15.211, J15.212, J15.29, J15.3, J15.4, J15.5, J15.6, J15.7, J15.8, J15.9, J16.0, J16.8, J17, J18.0, J18.1, J18.8, J18.9, J85.1
Upper respiratory tract infection	Adverse event - infection	Claims data	ICD-10 Diagnosis: J20.9, J00.0, J04.0, J06.0, J06.9, J02.9
Sepsis	Adverse event - infection	Claims data	ICD-10 Diagnosis: A02.1, A32.1, A40.7, A40.0, A40.1, A40.3, A40.8, A41.9, A41.01, A41.02, A41.1, A41.2, A41.3, A41.4, A41.50, A41.51, A41.52, A41.53, A41.59, A41.81, A41.89, A42.9, A54.7, B37.86, R65.7, R65.20, A22.21, A26.7, A41.7, A41., A41.0, A41.5, P36.8, P36.0, P36.10, P36.19, P36.2, P36.30, P36.39, P36.4, P36.5, P36.8

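### The upper respiratory tract infection code row includes an acute bronchitis code and a common-cold code that cannot match, and Table 2's Bronchitis and Sinusitis have no codes in Annex 2

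*Protocol*

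**What the plan says.** The row for upper respiratory tract infection in Protocol Annex 2 reads "ICD-10 Diagnosis: J20.9, J00.0, J04.0, J06.0, J06.9, J02.9". Table 3 (section 9.3) turns that row into a yes/no safety outcome. It is reported as prevalent and incident, with a 60-day washout for incident cases (footnote 2).

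Table 2 (section 9.3) defines the baseline variable Any infection by a list of types. Upper respiratory tract infection is one of them ("Other Pneumonia Upper respiratory tract infection Sepsis"). The list closes with "Candida esophagitis Urinary tract infection Sinusitis Bronchitis", so Sinusitis and Bronchitis are further types beside it.

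The Annex 2 entry for Any infection sends the reader to the individual code rows and closes with "Other infectious hepatitis, Helicobacter pylori, Candida esophagitis, Urinary tract infection". Sinusitis and Bronchitis are not in it, and neither has a code row anywhere in Annex 2.

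Section 9.8 makes these lists operative: "Clarify Health will code measures for cohort identification, outcomes, and other variables of interest based on codes and algorithms described in this protocol". It adds that the protocol will be followed strictly.

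**The concern.** A claims outcome is its code list. Two of the six codes in this row do not do what the label says, and the protocol's own tables disagree on where bronchitis belongs.

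J20.9 brings bronchitis into an outcome that Table 2 keeps apart from bronchitis. J00.0 is evidently meant to capture the common cold but would capture nothing. Table 2 also promises two infection types that the programmer has no codes for.

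At stake are the reported prevalence and incidence of upper respiratory tract infection under Exploratory Objective 1, in both the elranatamab and the teclistamab cohorts, and the baseline Any infection percentage. The abstract names infections as one of its adverse-event groups.

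**Working it through.** **Inputs.** The six codes come from the Annex 2 row. The infection types come from Table 2, Table 3 and the Annex 2 Any infection entry. The washout is from Table 3, footnote 2, and the prevalence and incidence formulas from section 9.7.6. Two facts come from the ICD-10-CM code set, which the protocol does not print: J20.9 is unspecified acute bronchitis, and J00 is a complete three-character code. Both are treated as assumptions that one lookup can confirm. The protocol states no figure for this outcome, so there is none to reproduce.

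**Step 1: the row.** One of six codes (J20.9) belongs to a type that Table 2 lists separately. One of six (J00.0) has no counterpart on claims. Four of six (J04.0, J06.0, J06.9, J02.9) work as intended.

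**Step 2: is J00.0 just house notation?** No. Annex 2 writes undivided codes bare (J13, J14 and J17 in the pneumonia row; R21 in the rash row) and marks whole families with an x (R50.x for pyrexia). Neither convention yields J00.0. A claim coded J00 does not match a listed string that is longer than itself, with or without the decimal point.

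**Step 3: the lists side by side.**

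| Place | Infection types | Sinusitis | Bronchitis |
|---|---|---|---|
| Table 2, Any infection | 17 | named | named |
| Annex 2, Any infection | 14 | absent | absent |
| Table 3, infection outcomes | 15 | absent | absent |

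The difference of 17 − 14 = 3 is COVID-19 pneumonia, Sinusitis and Bronchitis. COVID-19 pneumonia at least has its own code row; the other two have none. Bronchitis therefore enters these infection variables only through J20.9, under the upper respiratory label.

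**Step 4: effect on prevalence.** Call the four working codes the core.

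- a = share of patients with a J20.9 claim, no core code and no J00 claim
- b = share with a J00 claim, no core code and no J20.9 claim

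Prevalence as written − prevalence with the corrected row = a − b. Patients with any core code, or with both J20.9 and J00, are counted either way. The protocol gives neither a nor b, so neither the size nor the sign is known.

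**Step 5: effect on incidence.** Errors run in both directions:

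- J20.9 only, after index: a false incident case.
- J20.9 within 60 days before index, then a core code: a case wrongly removed.
- J00 only, after index: a case missed.
- J00 within 60 days before index, then a core code: a case that should have been washed out is kept.

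The net sign is again not derivable.

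**Step 6: effect on the baseline composite.** If Table 2 governs, J20.9 legitimately belongs in Any infection through Bronchitis. What is lost is J00, sinusitis and the remaining bronchitis codes. If the Annex list governs, J20.9 is surplus. The direction depends on which list is meant, and the protocol does not say.

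**Scale.** On the 133 patients with an elranatamab claim as of August 2024 (section 9.5), one misclassified patient moves a percentage by 100/133 = 0.75 points. That count precedes the eligibility criteria, and the final cohort will differ.

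**The case against.** The strongest reply is that this is a small code-list matter that leans on an outside code set. Table 3 has no bronchitis outcome, so nothing is double-counted after index. The list is printed, so a reader can see what was counted. The outcome is one of 15 infection rows under an exploratory objective, and no formal comparison is planned. Section 9.9 already warns that diagnosis codes may misclassify.

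Much of this stands, and it limits the weight of the point. It does not remove it. The conflict over bronchitis is internal once the code label is read. Section 9.9 speaks of how providers code, not of errors in the study's own list. Printing J00.0 does not tell a reader that it found nothing.

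Some stronger readings are tempting and are not supported:

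- A reader might infer that the missing sinusitis codes under-count upper respiratory tract infection. Table 2 makes Sinusitis a separate type, exactly as it does Bronchitis. The same logic that takes J20.9 out of the row keeps J01.x out.
- A reader might want the row widened to tonsillitis, further pharyngitis codes or the whole J00–J06 block. The protocol sets no standard for that; it is a choice of case definition.
- A reader might call this a frequent outcome. The protocol's only elranatamab figure is 69.9% for all infections (section 7); it gives none for upper respiratory infection.
- A reader might extend the point to time to infection onset. The infections covered by that analysis cannot be read in the text at hand, so this cannot be shown.

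**Conclusion.** The row is wrong as written in two of its six codes, and Table 2 and Annex 2 disagree on the Any infection types. Bronchitis-only patients will count as upper respiratory cases or be washed out of incidence, and common-cold claims will be missed. The size and net direction are unknown, and simultaneous over- and under-counting is possible but not quantified.

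The consequence is limited to one exploratory safety outcome, in each cohort, and one baseline composite; no primary outcome estimate depends on it beyond that baseline description. The conclusion assumes the ICD-10-CM meaning of J20.9, the undivided status of J00, and that the Annex 2 codes are applied as printed, as section 9.8 says. It is worth correcting because it is cheap and because the sponsor already treats such slips as amendable: Version 2.0 corrected J9415 to J9145 (section 5).

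**What to change.** In Annex 2:

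1. Remove J20.9 from the upper respiratory tract infection row.
2. Replace J00.0 by J00, after checking it against the code set.
3. Settle Bronchitis and Sinusitis in one of two ways. Either give each its own code row (J20.x for Bronchitis) and add both to the Annex 2 Any infection list, or delete both from Table 2. Under the second option, J20.9 leaves the baseline composite altogether, so the choice should be deliberate.

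Do not fold J01.x into the upper respiratory row; that would recreate for sinusitis the conflict now present for bronchitis.

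The cost is a few code rows and a re-run of one exploratory outcome and the baseline Any infection variable. If an interim delivery has already used the old row, a note that the definition changed is enough.

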1	Rheumatic disease	Medical claim with an ICD-10 code in the inpatient or non-IP setting for rheumatic disease (dichotomous)	180 days prior to index date to index
1	Peptic ulcer disease	Medical claim with an ICD-10 code in the inpatient or non-IP setting for peptic ulcer disease (dichotomous)	180 days prior to index date to index
1	Liver disease	Medical claim with an ICD-10 code in the inpatient or non-IP setting for liver disease (dichotomous)	180 days prior to index date to index
1	Diabetes	Medical claim with an ICD-10 code in the inpatient or non-IP setting for diabetes (dichotomous)	180 days prior to index date to index
1	Renal disease	Medical claim with an ICD-10 code in the inpatient or non-IP setting for renal disease (dichotomous)	180 days prior to index date to index date
1	Hemiplegia or paraplegia	Medical claim with an ICD-10 code in the inpatient or non-IP setting for hemiplegia or paraplegia (dichotomous)	180 days prior to index date
1	Human immunodeficienc y virus	Medical claim with an ICD-10 code in the inpatient or non-IP setting for human immunodeficiency virus (dichotomous)	180 days prior to index date to index date

Objective	Variable	Definition	Assessment Period(s)
1	Metastatic solid tumor	Medical claim with an ICD-10 code in the inpatient or non-IP setting for metastatic solid tumor (dichotomous)	180 days prior to index date to index date

Table 3 includes definitions and assessment periods for all study variables being used as outcomes. The full code list can be found in ANNEX 2. ADDITIONAL INFORMATION. If applicable, the frequency and percentage of patients with missing data for each variable will be described.

Table 3. Key Variables of Interest

Objective	Variable	Definition	Assessment Period(s)
Treatment ex	posure		
2	Use of supportive MM medications	Medical or pharmacy claim with evidence of an NDC, HCPCS, generic name or CPT code for the following medications (dichotomous):	Index date to the end of follow-up Index date Step-Up Dosing Period Maintenance Periods
2	Reported vial size	Reported vial size in the following categories (categorical): • Unknown vial – inpatient dose • 44mg/1.1mL • 76mg/1.9mL • Missing dose/unknown dose For the cohort of teclistamab patients the reported vial size (categorical): • Unknown vial – inpatient dose • 30mg/3mL • 153mg/7mL • Missing dose/unknown dose	Index date to the end of follow-up Index date Step-Up Dosing Period Maintenance Periods

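### Decimals in the Annex 2 sepsis row have slipped one place, so septic shock, candidal sepsis and five other intended codes are missing from the outcome definition

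*Protocol*

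**What the plan says.** Table 3 (section 9.3) defines the sepsis outcome of Exploratory Objective 1 as "Medical claim with an ICD-10 code in the inpatient, non-IP, or pharmacy setting for sepsis (dichotomous"). No other route of ascertainment is given. For codes the section defers to the annex: "The full code list can be found in ANNEX 2. ADDITIONAL INFORMATION".

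The Annex 2 sepsis row has 42 entries. It opens "A02.1, A32.1, A40.7, A40.0, A40.1, A40.3, A40.8, A41.9", continues through the A41 codes, then reads "A42.9, A54.7, B37.86, R65.7, R65.20, A22.21, A26.7, A41.7, A41., A41.0, A41.5, P36.8", and closes "P36.0, P36.10, P36.19, P36.2, P36.30, P36.39, P36.4, P36.5, P36.8".

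Section 9.8 has measures coded from the codes and algorithms in the protocol and adds: "This protocol will be strictly followed when conducting the analysis of this study". The amendment log (section 5) shows that v2.0 corrected one mistyped daratumumab code (J9415 to J9145). The sepsis row is not among the logged changes.

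**The concern.** Several entries do not fit their stems. A40.7 is printed ahead of A40.0. R65.7 stands beside R65.20. A22 carries a .21 that looks like the missing sibling of R65.20. There is a bare A41 with no decimal, and P36.8 is printed twice. This pattern suggests that the decimals moved against the stems when the list was compiled, not that single codes were mistyped.

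The row is used in three places: post-index sepsis prevalence and incidence (section 9.7.6), the 60-day washout for incident sepsis (footnote 2 to Table 3), and the baseline any-infection variable, whose Annex 2 entry points to the individual infection rows. Exploratory Objective 3 applies it to the teclistamab cohort as well. Serious infection is a central safety question for this drug: section 7 reports for the pivotal trial "common adverse events included infections (69.9%), cytokine release syndrome (57.7%), anemia (48.8%), and neutropenia (48.8"%).

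**Working it through.** No power or precision figure of the plan is involved, so there is nothing of that kind to reproduce. The check is structural, followed by a small illustration.

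**Step 1. Test for a shift.** Split each of the 42 entries into stem and decimal. Leave A02.1 as it is. From A32 onward, give each stem the decimal of the next entry. The result:

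| Printed | Realigned |
|---|---|
| A32.1 | A32.7 |
| A40.7, .0, .1, .3, .8 | A40.0, .1, .3, .8, .9 |
| A41.9, then .01 to .89 | A41.01 to .89, then .9 |
| A42.9 | A42.7 |
| A54.7 | A54.86 |
| B37.86 | B37.7 |
| R65.7, R65.20 | R65.20, R65.21 |
| A22.21 | A22.7 |
| A26.7 | A26.7 |
| A41.7, bare A41, A41.0, A41.5 | bare A41, A41.0, A41.5, A41.8 |
| P36.8, P36.0 … P36.5, P36.8 | P36.0 … P36.5, P36.8, then one P36 code without a decimal |

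One constant offset clears every anomaly. A40 and A41 run in ascending order, R65.20 and R65.21 stand together, P36.8 appears once, and the odd A41 entries become category headers. The decimal of A02.1 appears to have been repeated on A32, pushing all later decimals down one place, so that the last one fell off the end.

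**Step 2. Compare the two sets.**

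- In the realigned list but not printed: A22.7, A32.7, A40.9, A42.7, A54.86, B37.7 and R65.21, plus the header A41.8 (its children A41.81 and A41.89 are printed) and the final P36 code.
- Printed but absent from the realigned list: A22.21, A32.1, A40.7, A41.7, A42.9, A54.7, B37.86 and R65.7. In ICD-10, the code system the protocol names, A32.1 and A42.9 denote other conditions. The other six are not sepsis codes and would match no claim.
- Kept by coincidence: A41.9 (it received the .9 of A40.9), R65.20 and A26.7.

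Matching on prefixes would not recover the seven lost codes, because none of them begins with a printed entry. None appears in another infection row of Annex 2 either, so the baseline any-infection variable does not pick them up by another route.

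**Step 3. Direction.** Leaving aside stray matches on A32.1 and A42.9, prevalence can only fall. Incidence can move either way. A missed post-index event lowers it. A missed event in the washout lets a later A41 claim count as new, which raises it.

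**Step 4. Size, by assumption.** Let *p* be the true sepsis prevalence and *m* the share of sepsis patients identifiable only by a lost code. Reported prevalence = *p* × (1 − *m*). The protocol gives neither quantity, so both are assumed.

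| *p* | *m* = 5% | *m* = 20% |
|---|---|---|
| 5% | 4.75% | 4.0% |
| 10% | 9.5% | 8.0% |
| 15% | 14.25% | 12.0% |
| 20% | 19.0% | 16.0% |

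The only count in the protocol is 133 patients with an elranatamab claim as of August 2024 (section 9.5). At *p* = 15% that is 133 × 0.15 ≈ 20 patients with sepsis, of whom 20 × 0.05 = 1 to 20 × 0.20 = 4 would be missed. The 95% half-width at 15% is 1.96 × √(0.15 × 0.85 / 133) ≈ 6.1 percentage points.

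**The case against.** Four points deserve an answer.

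- **Reading fault.** Other rows of the annex, the musculoskeletal pain row for one, look garbled in the extracted text, so the sepsis row might be too. But garbling repeats or drops fragments. It does not move about 40 decimals by exactly one place and leave a coherent list once that is undone. The slip is in the list.
- **Code meanings.** The protocol does not label the codes, so septic shock and candidal sepsis are ICD-10 meanings. That is true, but the misalignment is shown from the row alone, and ICD-10 is the system the protocol relies on.
- **Size.** The A41 codes and R65.20 remain, so most bacterial sepsis is still caught, and septic shock with an accompanying A41 code is still counted. At 133 patients the illustrated loss of 0.75 to 3.0 points at 15% prevalence is below the half-width of about 6 points. This stands and limits the weight of the point. However, the loss is a systematic error that a larger cohort will not shrink.
- **Importance.** Sepsis is one of many exploratory events in a descriptive study, and no primary objective depends on it. Any-infection pools many types since the myeloma diagnosis and will hardly move. The duplicate P36.8 and the neonatal P36 codes are harmless in adults. All of this stands.

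None of it makes the printed row correct. The second-analyst review in section 9.8 does not promise validation of codes, and an analyst following the protocol strictly would apply the row as printed.

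**Conclusion.** The concern holds. One offset explains the whole row after its first entry. Seven usable sepsis codes are lost, septic shock and candidal sepsis among them, and eight wrong codes stand in the row. Because Annex 2 is the binding definition, sepsis prevalence would be understated in both cohorts, and incidence would be distorted by missed events and by patients who wrongly pass the washout.

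The size cannot be derived from the documents. It is probably modest and falls on fungal, listerial and unspecified streptococcal sepsis, the rarer causes, and shock recorded without an A41 code. The fall from 15% to between 14.3% and 12.0% rests on an assumed prevalence and an assumed 5% to 20% share coded only under lost codes. Section 9.4 bars reporting of counts from 1 to 10, so losing even a few patients could also push a small subgroup cell into suppression. The row should be corrected, although no primary objective is affected.

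**What to change.** Replace the sepsis row with: A02.1; A22.7; A26.7; A32.7; A40.0, A40.1, A40.3, A40.8 and A40.9; all A41 codes; A42.7; A54.86; B37.7; R65.20 and R65.21.

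Delete A22.21, A32.1, A40.7, A41.7, A42.9, A54.7, B37.86 and R65.7. Drop the P36 block as well, since inclusion requires age 18 or older. That last step is tidying and should change no result.

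Before the next data run, and at the latest before the final analysis planned for 27 February 2026, check the row by program against the ICD-10-CM files for the study years.

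The cost is a code-list edit, an amendment entry like the one made for J9145, and a re-run of the sepsis and any-infection variables in both cohorts. If interim results were produced with the printed row, restate their sepsis figures or mark them as not comparable with later ones.
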